COMIRB Protocol

COLORADO MULTIPLE INSTITUTIONAL REVIEW BOARD
[name] [contact] [contact]

Protocol #: 16-1785

Project Title: Evaluation of Moderate to Severe Influenza Disease in Children 6 months to 8 years in Colorado

Principal Investigator: [name]

Version Date: 7/27/16

I. Hypotheses and Specific Aims:

Children 6 months to 8 years of age with moderate to severe influenza have a higher risk of hospitalization, intensive care unit (ICU) admission, antibiotic use and complications compared with children with mild influenza illness.

Specific Aims:

Aim #1: To determine the validity of the moderate to severe endpoint for influenza as a predictor for hospitalization among children aged 6 months to 8 years evaluated at Children's Hospital Colorado (CHCO) emergency department (ED) and urgent cares (UC) during the 2016-2017 influenza season.

Aim #2: To prospectively evaluate the usefulness of the moderate to severe influenza endpoint against additional severity measures such as ICU admission, antibiotic and antiviral use, parental and child absenteeism and recurrent healthcare visits among children aged 6 months to 8 years evaluated at ED and UC centers in Colorado.

Aim # 3: To compare the healthcare costs associated with management of moderate to severe versus mild influenza disease.

Exploratory Objectives:

- 1) To compare the moderate to severe influenza definition, and other severity measures such as ICU admission, hospitalization, antibiotic, antiviral use, child and caregiver absenteeism among patients vaccinated with injectable influenza vaccine (IIV) versus unvaccinated individuals.
- 2) To evaluate severity measures such as hospitalization, ICU admission, antibiotic, antiviral use, caregiver and child absenteeism among children with influenza like illness who test negative for influenza.
- 3) To determine whether clinical measurements taken at ED/UC presentation such as systemic inflammatory response syndrome (SIRS) criteria, adjusted heart rate, oxygen saturation and temperature predict hospitalization, ICU admission and having polymerase chain reaction (PCR)-confirmed influenza. We will also consider the prediction value of peak temperature and temperature duration.

II. Background and Significance:

Influenza is an important cause of morbidity in children, annually causing 1-7 hospitalizations per 10,000 in US children under the age of 18 years (1-6). Children are

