The purpose of the proposed study is to validate that the definition of moderate to severe influenza in children predicts greater risk of healthcare endpoints such as hospitalization, increased length of stay, use of antimicrobials (including antivirals), absenteeism, increased duration of illness, and increased healthcare costs.

Understanding and validating the relationship between moderate to severe influenza and these clinically relevant endpoints is critical to establishing relevant surrogate markers of clinical and public health outcomes. If shown to be clinically relevant, this definition of moderate to severe influenza can be an important endpoint for assessing influenza vaccine effectiveness.

III. Preliminary Studies/Progress Report:

CHCO provides an ideal site for the study of influenza in children. CHCO is a large tertiary institution with a large catchment area of Denver Metro, Aurora and surrounding states. It serves 67% of children in the state of Colorado. From December 1, 2010 to April 30, 2014, there were 409 patients admitted to CHCO with PCR-confirmed influenza; 62% of these were defined as high-risk (16), and 38% were vaccinated against influenza during the same season. Accurate immunization data was available for 83% of patients via the Colorado Immunization Information System (CIIS). Clinical presentation and

hospital-based outcomes such as length of hospitalization among children admitted with influenza are shown in Table 1.

Table 1. Children Admitted To CHCO with Influenza, 2010-2014

Children admitted to CHCO with influenza N = 395	< 3 years N = 156	>3 years N = 239
Otitis media	10 (6)	6 (3)
Pneumonia	7 (5)	22 (9)
Hypoxia	19 (12)	141 (59)
Fever	133 (85)	207 (87)
Median duration of fever, days (range)	2 (1-17)	4 (1-64)
Tachypnea	64 (41)	91 (38)
Antibiotics	88 (56)	157 (66)
Median duration of antibiotics, days (range)	7 (0-23)	8 (0-77)
Pediatric Intensive Care Unit (PICU)	55 (35)	81 (34)
PICU length of stay, days	2 (1-100)	3(1-83)
Death	1 (1)	2 (1)
Median duration of hospitalization, days (range)	3 (1-100)	3 (1-128)
Vaccinated during current season against influenza	39 (25)	87 (36)

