For all study objectives, we will present data descriptively using frequencies for categorical variables and measures of central tendency for continuous variables. We will explore bivariable associations between moderate to severe versus mild influenza for covariates including demographic factors and clinical factors outlined above. Proportions will be compared using Chi-square test. Mean values will be compared using student's t test for normally-distributed data, otherwise Wilcoxon-Rank-Sum test will be used.

Aim #1/Primary Endpoint Analysis: We will use logistic regression to estimate odds ratios (and 95%CI) for hospitalization, adjusted for significant covariates at the level of $P < 0.2$ on bivariable analysis; and other covariates selected *a priori* that could affect outcomes such as hospitalization (age group, high risk medical condition, vaccination status, influenza type). We will verify to ensure statistical assumptions are met for each model. The intraclass correlation coefficient will be estimated and a multi-level model will be used if we need to account for multiple visits per child. If we use a multi-level model, the optimal covariance structure will be determined through the examination of information criteria statistics and graphical techniques.

Aim #2/Secondary Endpoint #1-6 Analysis: We will use logistic regression to estimate each of our dichotomous secondary outcomes of interest, ICU admission, antibiotic,

antiviral use, adjusted for significant covariates at the level of $P < 0.2$ on bivariable analysis; and other covariates selected *a priori* that could affect outcomes such as hospitalization (age group, high risk medical condition, vaccination status, influenza type). We will verify to ensure statistical assumptions are met for each model. The intraclass correlation coefficient will be estimated and a multi-level model will be used if we need to account for multiple visits per child. If we use a multi-level model, the optimal covariance structure will be determined through the examination of information criteria and graphical techniques. We will also explore our secondary outcomes of interest expressed as continuous variables (number of recurrent visits to the ED, duration of absenteeism in days). We will use a log linear model to compare these variables between the mild versus moderate to severe influenza groups and will exponentiate the coefficients to yield geometric mean ratios.

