Aim #3/Secondary Endpoint #7 Analysis: An economic analysis will be conducted to compare the healthcare costs in the mild and moderate to severe influenza groups. We will work with the finance department at CHCO to obtain charge data for each influenza-related ED visit and hospitalization. Direct costs associated with healthcare utilization will be obtained by collecting hospital charge data and applying a cost to charge ratio to estimate costs. Mean costs and standard deviations for each group will be determined and compared using t tests for normally distributed data, and presented as median (IQR) costs with analysis conducted using non parametric tests for non-normally distributed data. Relative healthcare costs will be modeled on log-transformed data using linear regression or a generalized linear model, depending on the data distribution.

Exploratory Objective #1-2/Exploratory Endpoints #1-2: In addition to the primary and secondary outcomes outlined above, we will also assess the odds ratios and 95% CI of several exploratory dichotomous outcomes –moderate to severe influenza, hospitalization, ICU admission, antibiotics and antiviral use among patients with IIV versus unvaccinated children using log linear regression in a manner similar to the above specific aims. For continuous variables (duration of fever, number of days of absenteeism), we will use a log linear model as described for our prior secondary outcomes.
We will conduct a similar analysis as outlined above for patients with influenza like illness who test negative for influenza using the clinical severity outcome measures outlined.

Exploratory Objective #3/Exploratory Endpoint#3: We will determine the predictive value for hospitalization, ICU admission and having PCR-confirmed influenza of duration of fever, SIRS criteria, adjusted heart rate, respiratory rate and oxygen saturation using logistic regression models with two-way interactions between factors in the model when needed. We will use the Brier score to assess overall model performance and the c statistic to assess discriminative ability. In addition to logistic regression, we will explore machine learning methods for the predictive modeling of these three outcomes. The predictive value of peak temperature will also be assessed using a logistic regression model.

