To compare temperature trajectories between hospitalized and non-hospitalized, we will use a linear mixed model. This will allow us to use all of the longitudinal temperature measurements to measure the mean temperature trajectory of patients in one group (e.g. hospitalized patients) compared to the other (e.g. non-hospitalized patients). We will accomplish this by including an interaction term between time and hospitalization status, which will give us hospitalization status-specific trajectories. We will do this for each

dichotomous outcome: hospitalization, ICU status, influenza diagnosis. This method is preferred over subgroup analysis because it will optimize statistical power.

[figure not shown]
Two sensitivity analyses will be conducted. Firstly, analyses will be restricted to patients presenting to the main CHCO ED. Secondly, to further evaluate whether temperature $> 39^{\circ}\text{C}$ is a predictor of healthcare utilization or poorer outcomes, an analysis of each of the secondary outcome measures will be conducted. Firstly, we will compare all moderate to severe versus mild influenza cases. If these reach statistical significance with an odds ratio > 1 , we will then repeat the analysis with a definition of moderate to severe influenza as solely temperature $> 39^{\circ}\text{C}$.

Power and sample size calculations:

Using historical data from our institution, a sample size of 408 patients (of which we assume 30% have mild flu and 70% have moderate/severe flu) will achieve 80% power at a 0.05 significance level to detect an odds ratio of approximately 2 for hospitalization among the moderate/severe compared to the mild cases, accounting for the inclusion of correlated covariables in our multivariable model. Assuming that 25% of patients tested will be influenza positive (19) during the influenza season; we will need to test approximately 1632 subjects (Figure 1). A sample size of 151 patients with the same assumptions, power and significance level will detect an odds ratio of 3 for hospitalization among the moderate/severe compared with mild cases, so 604 subjects will need to be tested.

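### Aim 1 asks whether the definition is a valid predictor of hospitalization, but its stated analysis (an adjusted odds ratio plus general descriptive tables) does not measure how well the definition discriminates

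*Combined protocol and SAP*

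**What the plan says.** Section I of the combined protocol and SAP words Aim 1 as "To determine the validity of the moderate to severe endpoint for influenza as a predictor for hospitalization among children" in the study's age range. Section II gives the longer-term motive: understanding this relationship "is critical to establishing relevant surrogate markers of clinical and public health outcomes", with possible later use of the definition as a vaccine-effectiveness endpoint.

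The Aim 1 paragraph of section IV.F states: "We will use logistic regression to estimate odds ratios (and 95%CI) for hospitalization, adjusted for significant covariates". The covariates are those passing a P < 0.2 bivariable screen, plus age group, underlying risk condition, vaccination and influenza type. The paragraph names no measure of classification or discrimination. The opening of IV.F adds, for every objective, that "we will present data descriptively using frequencies for categorical variables", and that proportions will be compared by chi-square.

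Performance measures do appear in IV.F, under Exploratory Objective 3: "We will use the Brier score to assess overall model performance and the c statistic to assess discriminative ability". They apply to models of "duration of fever, SIRS criteria, adjusted heart rate, respiratory rate and oxygen saturation using logistic regression models". Hospitalization is one of the outcomes there, but the moderate to severe definition is not among the predictors.

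**The concern.** An odds ratio says whether one group has higher odds of admission than another. Validity as a predictor also depends on how many admitted children the definition captures and how many non-admitted children it labels moderate to severe. A binary classifier that covers most of the sample can have a clearly significant odds ratio and still separate the two outcomes only a little better than chance.

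The plan recognises the distinction, because it attaches discrimination measures to predictive value in the exploratory objective. It does not do so for the definition that the primary aim sets out to validate. The Aim 1 odds ratio is also conditional on covariates, some chosen by a data-driven screen, whereas the definition itself is applied to a child without adjustment. If Aim 1 is reported through the adjusted odds ratio alone, readers who are considering the definition as a trial endpoint will not see how it performs by itself.

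**Working it through.** **Inputs from the documents** (IV.F, power and sample size paragraph): 408 influenza-positive children, 30% mild and 70% moderate to severe, target odds ratio about 2, 80% power, significance level 0.05. The companion figure is 151 children for an odds ratio of 3.

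**Inputs not in the documents:** the hospitalization risk in mild cases (p0), the R² for correlated covariates and the sidedness of the test. I assume p0 from 5% to 50% and a two-sided test.

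**The plan's own figures.** 408/0.25 = 1632 and 151/0.25 = 604 agree with the text. The 408 cannot be strictly reproduced without p0 and R². It is attainable with the Hsieh formula for logistic regression on one binary covariate (B = 0.70):

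- p0 = 0.21 with R² = 0 gives 405, and 151 for an odds ratio of 3.
- p0 = 0.25 with R² = 0.10 gives 408, and 154 for an odds ratio of 3.
- Pairs from about 0.20 with R² = 0 to 0.32 with R² = 0.17 match both stated figures within 3%.

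So 408 is not shown to be wrong, and it does not identify one value of p0.

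**Discrimination implied by the target.** Treat the odds ratio (OR) as crude, and let p1 be the risk in moderate to severe cases:

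- p1 = OR × p0 / (1 − p0 + OR × p0)
- overall risk P = 0.3 × p0 + 0.7 × p1
- sensitivity = 0.7 × p1 / P
- specificity = 0.3 × (1 − p0) / (1 − P)
- c = (sensitivity + specificity) / 2 for a binary classifier
- PPV = p1 and NPV = 1 − p0

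Worked case, p0 = 0.25 and OR = 2: p1 = 0.50/1.25 = 0.40. P = 0.075 + 0.280 = 0.355. Sensitivity = 0.280/0.355 = 0.79. Specificity = 0.225/0.645 = 0.35. c = 0.57. Risk difference = 0.40 − 0.25 = 0.15.

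| p0 (assumed) | p1 | Sensitivity | Specificity | c | PPV | NPV |
|---|---|---|---|---|---|---|
| 5% | 9.5% | 0.82 | 0.31 | 0.56 | 0.10 | 0.95 |
| 25% | 40% | 0.79 | 0.35 | 0.57 | 0.40 | 0.75 |
| 50% | 66.7% | 0.76 | 0.39 | 0.57 | 0.67 | 0.50 |

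The positive likelihood ratio runs from 1.18 to 1.24. At an odds ratio of 3, c is 0.59 to 0.62 over the same range. Because c hardly moves with p0, the unstated risk does not drive the result. PPV and NPV are almost wholly determined by it.

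**Smallest significant result.** With n = 408, a crude Wald test and a 122/286 split, the smallest significant observed odds ratio is 1.67 at p0 = 20% and 1.57 at p0 = 30%. The corresponding c is about 0.55 and specificity about 0.33. At p0 = 5% the threshold is higher, at 2.44 with c of 0.58.

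**The case against.** The strongest reply is that the plan uses validity in a narrower sense. The hypothesis in section I is that moderate to severe cases have a higher risk of admission, and the purpose in section II is likewise framed as greater risk. A between-group odds ratio with a confidence interval answers that. This stands: the odds ratio analysis is appropriate for the hypothesis and should stay. What it leaves open is the wording of Aim 1 itself and the surrogate-marker motive.

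Second, the planned frequencies and chi-square tests would probably yield the counts for a 2×2 table. This also stands in part. The information would be collected, but the plan derives no discrimination measure or interval from it.

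Third, the target odds ratio belongs to a multivariable model, while the figures above put it in a crude table. It is also an effect the study is sized to detect, not a forecast. Both are correct. The figures show what a result of that size could mean, not what the study will find. A full model could have a higher c, but part of that would reflect age and comorbidity.

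Fourth, if 70% of cases meet the definition, low specificity is partly built in. In the worked case, even if every admitted child met the definition, specificity could not exceed 0.30/0.645 = 0.47, and c could not exceed (1 + 0.47)/2 = 0.73. That is a reason to show the figures and interpret them against this ceiling.

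A reader might go further and infer that a significant odds ratio would by itself be declared proof of validity. The documents do not say so. Sections II and IV.G make later use conditional on the definition being shown clinically relevant, and Aims 2 and 3 add other outcomes.

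**Conclusion.** The point holds as a gap in the Aim 1 analysis, not as an error in it. The stated analysis tests higher risk. Beyond general descriptive tables, it does not report how well the definition separates hospitalized from non-hospitalized children.

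At the target odds ratio of 2, c would be 0.56 to 0.57, where 0.5 is chance, with sensitivity 82% to 76% and specificity 31% to 39%. This rests on three things: the plan's 70% share, the odds ratio read as crude, and an assumed mild-group risk of 5% to 50%.

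Two stronger readings are not supported:

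- One might quote a single PPV and NPV as following from the design. The mild-group risk is not stated, and the pair runs from about 10%/95% to 67%/50% over the assumed range, so no pair is design-based.
- One might conclude that the definition discriminates poorly. That is unknown until the data are in. The calculation shows only that a significant primary result would not rule it out.

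**What to change.** In the Aim 1 paragraph of IV.F, keep the adjusted odds ratio with its 95% CI as the test of higher risk. Add, for the definition alone against hospitalization in influenza-positive children, the unadjusted sensitivity, specificity, PPV, NPV, absolute risk difference and c statistic, each with a 95% CI. State that any conclusion that the definition is a valid predictor will be worded on both the association and the discrimination results.

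The additions come from a 2×2 table of data already being collected, and the c statistic is already used elsewhere in the plan. The cost is a few sentences, a small amount of analysis and possibly a more cautious conclusion. The measures would describe discrimination for admission. They would not by themselves establish the definition as a surrogate for vaccine effect.

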Preliminary data from the 2013-2014 and 2014-2015 influenza seasons demonstrated that among 11,997 patients who presented to CHCO ED, UC or outpatient clinics for an acute respiratory illness, 1398 (12%) underwent viral testing (either respiratory pathogen panel multiplex PCR or influenza PCR). 1375 patients were admitted for a respiratory illness, and of these, 994 (72%) underwent viral testing. Additional data regarding ED visits during these time periods are shown in Table 2.

Table 2. Children Presenting to CHCO ED or UC with Acute Respiratory Illness, 2013-2014 and 2014-2015

CHCO data:	2013-2014	2014-2015	Total
ED/UC/Clinic visits due to an acute respiratory illness	5900	6097	11997
ED visits due to an acute respiratory illness, limited to patients < 8 yrs	4510	4595	9105
ED visits limited to CHCO, Uptown Urgent Care, South Urgent Care with an acute respiratory illness, limited to patients < 8 yrs	2703	2809	5512
ED visits with above restrictions further limited to Jan to March	1290	1745	3035
Limit visits to < 8 yrs Jan to March, no repeat visits	1244	1688	2932
Admission for acute respiratory illness,	454	486	940

Jan -Mar

IV. Research Methods

The study comprises a prospective analysis of children presenting to CHCO ED, and North Campus UC with an influenza-like illness (ILI) during the 2016-2017 influenza season. Once enrolled in the study, we will collect respiratory samples (nasopharyngeal (NP) specimens), socio demographic, and clinical data including variables of interest outlined above, and follow the clinical outcome of these children for 14 days after their initial presentation. A complete list of the variables being collected can be found in Appendix A.

A. Outcome Measure(s):

Primary outcome measure /Endpoints:

- 1) Hospitalization in patients presenting to the CHCO Main ED or North Campus UC with influenza

Secondary outcome measures/Endpoints:

- 1) ICU admission in patients presenting to the CHCO Main ED or North Campus UC with influenza
- 2) Antiviral use in patients presenting to the CHCO Main ED or North Campus UC with influenza
- 3) Antibiotic use in patients presenting to the CHCO Main ED or North Campus UC with influenza
- 4) Number of visits to the ED or healthcare provider in patients presenting to the CHCO Main ED or North Campus UC with influenza
- 5) Number of days of absenteeism from school or daycare in patients presenting to the CHCO Main ED or North Campus UC with influenza

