- 2) Prior enrollment in study
- 3) Nurse only visit

C. Study Design and Research Methods

[figure not shown]
This will be a prospective observational cohort study conducted at the CHCO Main ED and North Campus UC.

Surveillance Methods:

The study group will review the CHCO Main ED or North Campus UC visits for patients meeting study criteria presenting with ILI. Screening will be conducted by designated professional research assistants (PRAs) at each site. The study team has a treatment relationship with potential subjects, since one of the co-investigators is an ED physician, thus enabling screening of potential patients. The parents/legal guardians of eligible patients will be approached for consent to obtain respiratory specimens for PCR testing, interviewed to obtain medical information pertaining to the current and future ILI visits, asked permission to obtain additional information (vaccination status, influenza vaccination type [LAIV] or IIV) and medical comorbidities) from the primary care provider, and to bank residual blood and respiratory samples. A memory aid card will be provided to the family member upon discharge from the ED/UC setting as an aide memoire, and the medical chart will be reviewed for additional clinical and demographic information. On day 14(+/-3) following the initial visit, caregivers of all participants who test positive for influenza will be contacted by phone to provide additional follow-up information regarding child and parental absenteeism, additional healthcare visits, duration of illness. Additionally, a random sample of participants whose influenza test is negative in a 1 to 4 ratio will be contacted for follow-up. A second chart review will occur at this time for details regarding additional visits or admissions. Data will be managed with REDCap (Research Electronic Data Capture) tools hosted at the University of Colorado (19) and exported to SAS 9.3 (Cary, NC) for statistical analyses.

A flow diagram summarizing the study methods is shown in Figure 1.

Figure 1. Flow diagram summarizing methods for proposed surveillance study

Specimen Testing:

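### Enrolment site (hospital ED or urgent care) is not a pre-specified covariate, so adjustment of the pooled severity odds ratio for site is not assured

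*Combined protocol and SAP*

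**What the plan says.** Section IV.C describes the setting: "This will be a prospective observational cohort study conducted at the CHCO Main ED and North Campus UC". The primary outcome in IV.A pools both places: "Hospitalization in patients presenting to the CHCO Main ED or North Campus UC with influenza".

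In IV.F, the Aim #1 model and the Aim #2 models for dichotomous outcomes take covariates by two routes:

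- An a priori list: "age group, high risk medical condition, vaccination status, influenza type".
- A data-driven route: "adjusted for significant covariates at the level of" P < 0.2 on bivariable analysis. The opening paragraph of IV.F describes that bivariable analysis as comparing moderate-to-severe with mild influenza "for covariates including demographic factors and clinical factors outlined above".

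The multi-level option concerns children, not sites: "a multi-level model will be used if we need to account for multiple visits per child". The log-linear models for visit counts and absenteeism (Aim #2) and the cost models (Aim #3) name no covariates.

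Site appears once in IV.F, among the sensitivity analyses: "Firstly, analyses will be restricted to patients presenting to the main CHCO ED".

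**The concern.** A hospital ED and an urgent care are different kinds of setting. Admission practice and severity mix may well differ between them. If the same site is higher on both, part of the pooled association between the moderate-to-severe definition and hospitalization is an association between site and hospitalization. Aim 1 would then credit the definition with predictive value that belongs partly to where the child was seen. This matters because sections II and IV.G present the study as support for using the definition as a vaccine-effectiveness endpoint.

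As written, two analysts following IV.F could differ on whether site is a candidate for the screen, and so report different headline odds ratios. The plan also does not say what follows if the pooled and ED-only results disagree.

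**Working it through.** **Inputs from the documents (IV.F, Power and sample size calculations).** 70% moderate-to-severe and 30% mild; target odds ratio about 2; 408 influenza-positive children.

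**Inputs not given, therefore assumed.** The share of cases from each site, the severity mix and admission rate at each site, and the hospitalization rate in the cohort. I take about 30% hospitalized overall. Table 2 has 940 respiratory admissions beside 2,932 non-repeat visits (940/2932 = 32%), but that covers all acute respiratory illness and the two counts may not share a denominator.

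**The plan's own figures.** The plan gives no figure for a site effect. Its testing numbers reproduce: 408/0.25 = 1632 and 151/0.25 = 604. The 408 cannot be derived from the stated inputs, because the mild-group hospitalization rate and the covariate R² are missing. It is attainable: a mild-group rate of 21% with R² of 0 to 0.01 gives 405 to 409. That pair is not unique. It implies 0.3 × 0.21 + 0.7 × 0.347 = 31% hospitalized overall, so 30% is a reasonable working value. This point does not dispute the 408.

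**Formula.** Let w be the ED share of cases, m the moderate-to-severe proportion at a site, h the proportion admitted there, and θ the true within-site odds ratio. At each site, solve for the mild-group risk a in (1−m)a + mb = h, where b = θa/(1−a+θa) is the moderate-to-severe risk. Then collapse over site (E = ED, U = urgent care):

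- Moderate-to-severe risk = [w·mE·bE + (1−w)·mU·bU] / [w·mE + (1−w)·mU]
- Mild risk = [w(1−mE)aE + (1−w)(1−mU)aU] / [w(1−mE) + (1−w)(1−mU)]

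The pooled odds ratio compares these two risks.

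**Worked case, θ = 1 (scenario D).** w = 0.70, m = 0.75 and 0.58, h = 0.40 and 0.07.

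- Moderate-to-severe: (0.525 × 0.40 + 0.174 × 0.07)/0.699 = 0.318
- Mild: (0.175 × 0.40 + 0.126 × 0.07)/0.301 = 0.262
- Pooled odds ratio: (0.318/0.682)/(0.262/0.738) = 1.31, although severity has no effect at either site

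**All scenarios (30% hospitalized and 70% moderate-to-severe overall, to rounding).**

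| | ED share | Mod/severe, ED v UC | Admitted, ED v UC | Site OR for admission | True 1.0 appears as | True 2.0 appears as |
|---|---|---|---|---|---|---|
| A | 70% | 73% v 63% | 35% v 18% | 2.5 | 1.09 | 2.12 |
| B | 70% | 75% v 58% | 35% v 18% | 2.5 | 1.15 | 2.23 |
| C | 70% | 73% v 63% | 40% v 7% | 8.9 | 1.17 | 2.18 |
| D | 70% | 75% v 58% | 40% v 7% | 8.9 | 1.31 | 2.43 |
| E | 60% | 80% v 55% | 45% v 7.5% | 10.1 | 1.71 | 3.03 |
| F | 70% | 70% v 70% | 40% v 7% | 8.9 | 1.00 | 1.87 |

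Scenario F has equal case mix. There is no confounding, and the fall from 2.0 to 1.87 is non-collapsibility of the odds ratio alone.

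A separate grid (50:50 enrolment, 8% mild-group admission at the urgent care, site odds ratio 2 to 8) gave 1.09 to 1.24 for a true 1.0 with mix 75% v 65%, and 1.18 to 1.57 with 80% v 60%. The table's range is not a bound: with 70% from the ED, mix 73% v 63%, 8% at the urgent care and a site odds ratio of 2, a true 1.0 appears as only 1.06.

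**Would the P < 0.2 screen catch it?** Only if site is treated as a candidate. In that case, with 408 children and a normal approximation to the two-proportion test, site would pass with probability about 98% for 75% v 58%, roughly three in four for 73% v 63%, and almost 100% for 80% v 55%.

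**Price of adjusting.** The squared site–severity correlation is w(1−w)(mE−mU)²/(0.7 × 0.3): 0.010, 0.029 and 0.071 for the three unequal mixes. Then 408/(1−R²) is about 412, 420 and 439.

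**The case against.** A reader might infer that site is barred from the model. The text does not support that. The description of the covariates is open-ended, demographic and clinical factors being examples, and most of the variable list in Appendix A is not in the text available here. If site is a candidate, the screen would very probably admit it in the scenarios with the largest bias. This stands, and it reduces the concern to one of assurance: the plan does not say that site is a candidate, and the smaller mix gap would be missed about one time in four.

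A reader might also infer that site has been overlooked. It has not. Restriction to the ED removes ED-versus-urgent-care confounding from that estimate, and comparing it with the pooled result would be informative. But it discards the urgent care children (if 70% of cases came from the ED, 408 becomes about 286) and does not change the headline estimate.

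Third, Aim 1 can be read as a question of prediction in the pooled population. If caregivers choose the site by how ill the child seems, adjusting for site removes some true severity signal. This also stands, and it is the reason to report both estimates rather than replace one with the other.

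Finally, the larger figures need admission odds ratios of about 9 to 10 between sites, and all are crude. Adjustment for age group and high-risk condition may absorb part of a case-mix difference.

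**Conclusion.** The gap is real and modest. Enrolment site is not a pre-specified covariate for Aims 1 and 2, no stratification or clustering by site is planned, and the one planned analysis that addresses site leaves the headline odds ratio pooled.

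It would be too strong to say that the planned odds ratio is biased. Confounding needs the sites to differ in both severity mix and admission after the other covariates are adjusted for, and bias away from the null needs the same site to be higher on both. The documents contain no site-specific figure that shows either. On the stated assumptions, a true odds ratio of 1.0 would appear as about 1.09 to 1.71, with the milder assumptions at 1.09 to 1.15. With equal mix, a true 2.0 would be slightly attenuated, to about 1.87. Against a design target of about 2, the upper part of that range would change the reading of Aim 1 and the lower part would not.

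The same reasoning may carry over to the secondary outcomes and costs, but nothing in the documents allows a size to be put on it there.

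**What to change.** In IV.F, add enrolment site (Main ED or North Campus UC) to the a priori covariates of the Aim 1 and Aim 2 models, including the log-linear models, and to the Aim 3 cost model. Define site by first presentation, so that a child sent on from the urgent care to the ED keeps the urgent care label. Report the estimate without site beside the site-adjusted one, and keep the ED-only sensitivity analysis.

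The cost is a sentence or two in the plan and one parameter, from a variable known for every child. In the scenarios above, the equivalent sample size rises from 408 to between 412 and 439. The plan says it already allows for correlated covariables, which may cover this. The other cost is the possible loss of true severity signal if families choose the site by perceived severity; showing both estimates makes that visible.
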